Affected Subjects: Adolescents (ages 9-21 years) with a current DSM-IV-TR diagnosis of MDD or Depressive Disorder NOS (defined as exhibiting 4 of 5 criteria for an episode of major depression or meeting all MDD criteria except duration) will be recruited from the University of Cincinnati BITREC “at-risk” cohort (n=140, UC-IRB #07-04-10-03) of adolescent offspring of parents with bipolar I disorder. To be included in the BITREC at-risk cohort, adolescents must have no lifetime syndromal mood or psychotic disorder at their initial baseline assessment, a parent with bipolar I disorder, and no contraindication to undergoing an MRI scan. Based on data from prior studies we estimate that at least 35% of the cohort will develop MDD within the 5-year longitudinal follow-up period of BITREC.⁶ Subjects for the proposed study will be recruited from the “at-risk” cohort as well as from adolescents who have already developed MDD or Depressive Disorder NOS and who are screen failures for the BITREC “at-risk” cohort. The BITREC at-risk adolescents in the BITREC are evaluated monthly for follow-up and are instructed to call study staff between visits if mood symptoms emerge, so that we will be able to identify potential subjects for the proposed study at or soon after the onset of a mood disorder. If a subject is recruited from outside of BITREC, their biological parent(s) with bipolar I disorder will be asked to complete a Structured Clinical Interview for DSM Disorders (SCID) to confirm diagnosis of bipolar I disorder. One of the main goals of BITREC is to identify neurobiological changes that occur prior to and at the onset of a mood disorder in adolescents who have a parent with bipolar I disorder. Therefore, all at-risk adolescents who develop a mood disorder will undergo a ¹H MRS as part of their participation in the BITREC, which is identical to the MR scans proposed for this study. This scanning session will occur during the baseline study visit for the proposed study for eligible BITREC subjects who choose to participate in the proposed trial. The omega-3 treatment trial and the week 12 MRS scan will occur exclusively as part of this study and are distinct from, although complementary to, participation in the BITREC. As part of the BITREC longitudinal illness course assessments are performed in the at-risk adolescents. However, the BITREC does not include a systematic treatment study for these individuals, other than for those who develop mania, who will be excluded from participation in the proposed study. We will give all participants the opportunity to participate in BITREC at study termination in order to provide follow-up.

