The ADHD Rating Scale (ADHD Rating Scale-IV),^{46,47} completed by the parent or guardian, will be administered at screening, baseline, and each weekly visit and will be used to assess ADHD symptom severity during the prior week. Rates of ADHD are high in adolescents at risk for developing mania and who have a parent with bipolar disorder.^{6,48} Therefore, excluding these adolescents would limit the generalizability of our findings. Moreover, data suggest that omega-3 fatty acids may be effective for the treatment of ADHD symptoms.⁴⁹⁻⁵² Thus, we will include adolescents with ADHD in our study. However, to be included the adolescent must have been taking a stable dose of psychostimulants during the month prior to baseline.

The Columbia Suicide Severity Rating Scale (C-SSRS)⁵⁶, will be administered by trained raters at each visit as a measure of suicidality. All study investigators and staff have received training from one of the authors of the C-SSRS, [name] at Columbia University. We have incorporated this rating scale into several other studies of adolescents with mood disorders. If any subject experiences worsening of suicidality during the course of the study, they will be discontinued from study participation and receive appropriate clinical care.

The Children's Global Assessment Score (CGAS)⁵⁷ will be administered by a child and adolescent psychiatrist at screening, baseline, weeks 4, 8, and 12 (or termination), and the follow-up visit at week 14, will be used to assess overall function at the time of the rating.

Additionally, psychosocial function during the month prior to baseline will be assessed using the functional rating scales of the Longitudinal Interval Follow-up Evaluation (LIFE).^{58,59} Trained raters with good inter-rater reliability ($\kappa > 0.8$) will evaluate each of four major areas of functioning; role performance, interpersonal relationships, recreational enjoyment, and sexual activity. To assess change in function, the same rater will evaluate each of these four major areas for the prior 4-week period at weeks 4, 8, and 12 (or termination).

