group2)/pooled standard deviation. We will use a χ^2 test to compare percent responders (defined by CGI-I ≤ 2) at endpoint between treatment groups.

Prediction 2: Omega-3 fatty acid supplementation will be more effective than placebo for improving behavioral symptoms and psychosocial functioning in adolescents with a high risk for developing mania. A MMRM approach will be used to compare change over time in ADHD-RS scores between treatment groups. Additionally, change over time in CBCL and TRF externalizing and internalizing t-scores will be examined using a MMRM model. We will use a χ^2 test to determine whether the percent of subjects > 18 years old (vs. ≤ 18 year old) with completed CBCL and TRF ratings differs significantly between treatment groups. If there is no statistically significant difference, T-scores for 19-21 year olds will be determined using the gender-specific 18 year old t-scores, since we will be examining for group differences in change in score over time. We will use generalized linear mixed logistic regression models to examine change over time in percent responders (defined by achieving a level of functioning that is equal to or better than the month prior to baseline) in each of the four major areas of functioning; role performance, interpersonal relationships, recreational enjoyment, and sexual activity. A mixed effects model repeated measures (MMRM) approach will be used to compare change over time in CGAS scores between treatment groups. We will also evaluate change from baseline to endpoint in CGAS scores and calculate effect sizes as described. Covariates will be included in these models as described above. Additionally, we will examine the effect of change in mood symptom ratings during a specific time period (YMRS and CDRS-R) on change in behavioral and psychosocial functioning during the same time period by using, a repeated-measures framework in SAS PROC MIXED to account for the fact that multiple observations per individual on the same outcome are correlated across time.

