Patients: This is a 12-week double-blind randomized investigation of omega-3 fatty acid (N=30) vs. placebo (N=30) for the treatment of major depressive disorder and depressive disorder NOS in adolescents (N_{Total}=60). Patient selection will be done by research staff in consultation with and with permission from the PI. Inclusion/Exclusion criteria are found below (see F., 3.).

Healthy Controls: Although we will not recruit healthy subjects for the proposed study, they are recruited (n=40) already for BITREC Project 3 and undergo an initial ¹H-MRS scan. Therefore, we will be able to interpret the direction of neurobiological changes in at-risk adolescents (i.e., whether patient values are changing toward or away from those of healthy adolescents).

2. Estimated sample size: We propose to randomize 30 subjects per treatment group, for a total of 60 subjects at the University of Cincinnati. As this is an investigator-initiated protocol, there are no other sites associated with this submission.

Based on our prior studies, we estimate that approximately 25% of patients will either discontinue study participation prior to completing study procedures or will not have usable MRS data. For the power calculations described, we considered medium to large effect sizes of $d > 0.6-0.8$ to be clinically relevant.⁷⁹

3. Description of Inclusion/Exclusion Criteria

Inclusion Criterion:

- Ages 9 -21 years old.
- At least one biological parent with bipolar I disorder.
- Meets DSM-IV-TR⁸⁰ criteria for major depressive disorder (MDD) or Depressive Disorder NOS at screening as determined by the Washington University at St. Louis Kiddie Schedule for Affective Disorders and Schizophrenia, WASH-U-KSADS;⁸¹
- Childhood Depression Rating Scale-Revised Version^{40,41} (CDRS-R) scores ≥ 28 at screening and baseline.
- Fluent in English.
- Provision of written informed consent/assent as previously described.
- Agrees to use one of the following method of birth control: complete abstinence from sexual intercourse, barrier (diaphragm or condom), or oral/injectable contraceptive.

Exclusion Criterion:

- Contraindication to an MRI scan (e.g., metal clips, braces or claustrophobia).
- Mood symptoms resulting from acute medical illness or acute intoxication or withdrawal from drugs or alcohol as determined by careful medical evaluation or rapid symptom resolution.
- Psychotic symptoms (i.e., hallucinations or delusions).
- Any lifetime history of a manic or hypomanic episode.

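### The LIFE psychosocial responder rule counts unchanged patients, so it compares non-worsening between arms and not the improvement that Prediction 2 claims

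*Combined protocol and SAP*

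**What the plan says.** In section E.b (Data Analyses), Prediction 2 of the combined protocol and SAP states the claim: "Omega-3 fatty acid supplementation will be more effective than placebo for improving behavioral symptoms and psychosocial functioning". For LIFE, the same paragraph specifies generalized linear mixed logistic models for each of four areas (role performance, interpersonal relationships, recreational enjoyment, sexual activity), with the outcome "percent responders (defined by achieving a level of functioning that is equal to or better than the month prior to baseline".

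The Assessments part of section E.a fixes the reference. At baseline, "psychosocial function during the month prior to baseline will be assessed using the functional rating scales" of the LIFE. The follow-up ratings, made at weeks 4, 8 and 12 or termination, have a stated purpose: "To assess change in function, the same rater will evaluate each of these four major areas for the prior 4-week period".

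The LIFE sentence does not itself mention a comparison of arms. Treatment group enters through the statement that covariates are included as described above, which leads back to Prediction 1, where the covariates are study week and treatment group. Overall function is handled differently: an MMRM is used to "compare change over time in CGAS scores between treatment groups", with baseline-to-endpoint change and effect sizes in addition.

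**The concern.** The rule sets the bar for response at the level the patient already had on entry. A depressed adolescent whose functioning stays the same at weeks 4, 8 and 12 is a responder at every visit. The logistic model therefore compares the proportion *not worse*, while the prediction concerns the proportion or degree *better*.

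Two errors can follow. If omega-3 moves patients from unchanged to improved without altering how many worsen, the analysis shows no difference in any area, and modelling more visits does not help. Conversely, if omega-3 only prevents worsening, the analysis reports a difference in response although no more patients improved. A pilot's response percentages feed later planning, so either error carries forward. The label adds to the problem: Prediction 1 uses responder for CGI-I ≤ 2, which is an improvement criterion, so one word would stand for two different things.

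**Working it through.** **What the rule measures.** Let I, S and W be the proportions improved, the same and worse relative to the pre-baseline month, with I + S + W = 1. The plan's responder rate is R = I + S = 1 − W. The arm difference is

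R(omega-3) − R(placebo) = W(placebo) − W(omega-3).

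I drops out. If nobody in the trial changes, both arms score 100%. At baseline R is 100% by construction, so the percentage of responders can only stay level or fall from there. This step needs no assumed number.

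**Is there another LIFE comparison?** Functioning appears in three other places in E.b: the model relating change in mood ratings to change in psychosocial functioning (Prediction 2), the expanded metabolite path models that mention functional ratings (Prediction 4), and the exploratory analyses relating functional change to biomarkers. None states a comparison of LIFE ratings, or of strictly improved patients, between arms.

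**Size.** The plan gives no LIFE response rate or LIFE power, so there is no figure to reproduce.

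- From the documents: 30 per arm; a loss where "approximately 25% of patients will either discontinue study participation prior to completing study procedures or will not have usable MRS data" (section F.2), giving 30 × 0.75 = 22.5, taken as 22; effect sizes of 0.6–0.8.
- Assumed: all LIFE proportions, two-sided 0.05, and one time point in place of the repeated-measures model.
- Method: exact enumeration of the uncorrected chi-square test. The ordinal comparison is a tie-corrected rank-sum test on worse/same/improved, with 20,000 simulations.

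*Case 1: equal worsening.* W = 10% in both arms; I = 30% on placebo and 60% on omega-3. Then R = 1 − 0.10 = 90% in both arms.

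| Outcome | Placebo vs omega-3 | 30 per arm | 22 per arm |
|---|---|---|---|
| Plan's rule | 90% vs 90% | 5.4% | 4.3% |
| Improved | 30% vs 60% | 66% | 52% |
| Ordinal | 10/60/30 vs 10/30/60 (worse/same/improved) | 52% | 40% |

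*Case 2: the whole distribution shifts.* A latent normal score with placebo cut-offs at −1 (worse below) and 0.5 (improved above) gives placebo W = Φ(−1) = 15.9% and I = 1 − Φ(0.5) = 30.9%. Under a shift d, R = 1 − Φ(−1 − d) and I = 1 − Φ(0.5 − d).

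| | d = 0.6 | d = 0.8 |
|---|---|---|
| R, placebo vs omega-3 | 84.1% vs 94.5% | 84.1% vs 96.4% |
| I, placebo vs omega-3 | 30.9% vs 54.0% | 30.9% vs 61.8% |
| Power, plan's rule (30 / 22 per arm) | 27% / 19% | 39% / 26% |
| Power, improved (30 / 22) | 45% / 34% | 69% / 55% |
| Power, ordinal (30 / 22) | 51% / 39% | 74% / 61% |

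*Case 3: range at 30 per arm.* With placebo worsening between 10% and 30%, the plan's rule has 17–36% power at d = 0.6 and 22–54% at d = 0.8. With placebo improvement between 20% and 40%, the improved rule has 41–46% and 65–69%.

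*Case 4: the opposite error.* With improvement of 30% in both arms and worsening of 5% on omega-3 versus 30% on placebo, the rule reports 1 − 0.05 = 95% versus 1 − 0.30 = 70% responders, a 25-point difference in response with no difference in improvement.

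**The case against.** The strongest defence is that reaching a prior level of function describes recovery. BITREC participants may be enrolled "at or soon after the onset of a mood disorder" (section E.a, Affected Subjects), so part of the reference month may precede the illness, and an equal rating may then partly mean regained function. This stands as a partial rationale. But the reference month is not defined as premorbid, it ends at an ill baseline, and recruitment also takes adolescents who already have the disorder.

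Second, improvement is still tested elsewhere: CGAS, ADHD-RS, CBCL and TRF are all analysed as scores by MMRM. This stands and limits the reach of the point. Prediction 2 as a whole is not left untested; its four LIFE areas are. A single global score such as CGAS does not replace them.

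Third, the LIFE sentence never says between treatment groups. That is true, and the between-arm reading rests on the covariate cross-reference. If no arm comparison were meant, LIFE could not address a claim of superiority over placebo at all. The path models do include treatment group and mention functional ratings, but they name neither instrument nor coding and concern metabolite effects.

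Fourth, the figures are illustrative. All rates are assumed, and Case 1 produces the null result by construction. The 25% loss mixes discontinuation with unusable MRS data, and the latter does not remove a LIFE rating, so 22 per arm is a lower bound. At d = 0.6 the loss can be small: the plan's rule reaches 36% at one end of its range and the improved rule is 41% at the low end of its own. These points qualify the size and leave the mismatch untouched.

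**Conclusion.** The concern holds. As written, the LIFE responder analysis measures absence of worsening, and Prediction 2 claims improvement. That follows from the definition alone. How much sensitivity is lost depends on LIFE distributions that the documents do not give. Under the assumptions shown, at 30 per arm, the rule has no power beyond the test's nominal error rate when worsening is equal in the arms, and 27% or 39% against 45% or 69% for strict improvement when the whole distribution shifts by 0.6 or 0.8 SD. This should be fixed, but it affects one of several Prediction 2 measures in a 60-patient pilot and does not threaten the trial.

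**What to change.** Compare the LIFE area ratings at weeks 4, 8 and 12 between arms with a cumulative-logit mixed model adjusted for the pre-baseline rating, and state the treatment contrast explicitly. Alternatively, define response as a rating better than in the month before baseline. Keep the present rule only as a separate result named *not worse*, so that it cannot be confused with improvement or with CGI-I response.

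The cost is SAP wording and a re-coded variable; visits, ratings and sample size do not change. Each option has a small drawback. Under the improvement dichotomy, patients already at the best level cannot respond, although they remain informative in the ordinal model. The ordinal comparison can lose power to the dichotomy when worsening is equal in the arms (52% against 66% in Case 1), but it did better under the latent shift. The choice should be fixed before unblinding.

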Prediction 3: Omega-3 fatty acids will be safe and well tolerated compared with placebo. To evaluate the safety and tolerability of omega-3s we will use ANOVAs to compare change from baseline to week 12 (or endpoint) in vital signs and laboratory values. Additionally, we will determine the percentage of subjects who reported each adverse event and will examine treatment group differences in adverse events and serious adverse events using Fisher exact or χ^2 tests.

Prediction 4: Improvement in mood symptoms following treatment with omega-3 fatty acids is mediated by decreases Glu and mI levels and increases in NAA levels in the VLPFC (BA 10) and ACC (BA 24, 32). Our hypothesized model predicts that treatment produces changes in metabolite levels (Glu, mI, and NAA). These metabolite changes lead to change in mood symptoms. The mediated link between treatment and mood symptoms via metabolite levels is the *indirect treatment effect*. The *direct treatment effect* represents any residual association between treatment and mood symptoms after adjusting for the *indirect effect*. This association will be smaller in magnitude than the unadjusted association between treatment and mood symptoms (which is the *total treatment effect* or the quantity of interest in Prediction 1). For the prediction of a mediated treatment effect to be supported, two conditions must be met, i.e., significant associations between treatment and metabolite levels and between metabolite levels and mood symptoms. Prediction 4(a) is that treatment with omega-3 fatty acids will lead to decreases in Glu and mI levels and increases in NAA levels within VLPFC and ACC. It is possible for this prediction to be supported in the absence of a general association between treatment and mood symptoms (Prediction 1), which would suggest that these metabolic changes do not impact clinical outcome. Prediction 4(b) is that decreases in Glu and mI levels in VLPFC and ACC, and increases in NAA in VLPFC and ACC, will lead to decreases in

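### Prediction 3 claims acceptable safety relative to placebo, but the only planned comparisons are difference tests at 30 per arm, with no between-group estimate, interval or margin; a non-significant result could not support it

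*Combined protocol and SAP*

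**What the plan says.** Section E.b (Data Analyses), Prediction 3, is that "Omega-3 fatty acids will be safe and well tolerated compared with placebo". The evaluation has three parts:

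- For continuous measures: "we will use ANOVAs to compare change from baseline to week 12 (or endpoint) in vital signs and laboratory values".
- For description: "we will determine the percentage of subjects who reported each adverse event".
- For comparison of events, the investigators "will examine treatment group differences in adverse events and serious adverse events using Fisher exact or" chi-square tests.

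Prediction 3 names no acceptable excess, risk difference, confidence interval, significance level or rule for when the prediction counts as supported. By contrast, Predictions 1 and 2 plan standardized effect sizes for the CDRS-R, YMRS and CGAS.

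On size, section F.2 says: "We propose to randomize 30 subjects per treatment group, for a total of 60 subjects at the University of Cincinnati". It expects that "approximately 25% of patients will either discontinue study participation prior to completing study procedures or will not have usable MRS data", and the effect sizes it treats as clinically relevant are d of 0.6 to 0.8. It gives no AE rate. Section G.1 says only, in general terms, that earlier omega-3 studies were well tolerated.

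**The concern.** The prediction and its analysis point in different directions. Being safe compared with placebo is a statement that any excess harm is small enough to accept. The Fisher, chi-square and ANOVA tests ask whether there is evidence that the arms differ. A significant excess would count against the prediction. A non-significant result says little unless the study could have excluded an excess that matters, and the plan gives no quantity that would show this.

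At stake is what can be written about safety at the end of a trial in participants aged 9 to 21, where safety and tolerability are part of Aim 1. With a p-value as the only comparative output, a reader cannot see how large an excess remains compatible with the data.

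**Working it through.** **Inputs.** 30 per arm, allocated 1:1 (section F.2). Fisher exact or chi-square for events (section E.b, Prediction 3). *Assumptions:* two-sided 0.05, because no level is stated for Prediction 3, and AE rates of 0% to 30% on placebo with a range of excesses, because the documents give none. The plan states no power or margin for safety, so there is no planned figure to reproduce.

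**1. Power of the Fisher test at 30 per arm.** Sum the product of two binomial probabilities over all pairs (x₁, x₂) for which the two-sided Fisher p is at most 0.05:

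Power = Σ Bin(x₁; 30, p₁) · Bin(x₂; 30, p₂) · 1[p_Fisher(x₁, x₂) ≤ 0.05]

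| Placebo v omega-3 | Fisher | Chi-square, uncorrected |
|---|---|---|
| 10% v 20% | 10% | 19% |
| 20% v 40% | 30% | 39% |
| 10% v 30% | 37% | 50% |
| 5% v 25% | 44% | 63% |
| 0% v 20% | 57% | 88% |
| 5% v 30% | 63% | 78% |
| 10% v 40% | 71% | 80% |

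Chi-square does better for rare events, but there the expected counts fall below 5 and Fisher would normally be used. Fisher reaches 80% power at 25.5% v 0%, 35.5% v 5%, 44% v 10% and 58% v 20%, that is, at excesses of about 25 to 38 points. Significance requires 6/30 v 0/30, or 11/30 v 3/30.

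**2. What a non-significant result leaves open.** The Newcombe 95% interval for d = p₁ − p₂, with Wilson limits (l, u) for each arm, is:

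lower = d − √[(p₁ − l₁)² + (u₂ − p₂)²]; upper = d + √[(u₁ − p₁)² + (p₂ − l₂)²]

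- *6/30 v 2/30.* p₁ = 0.200 (0.095, 0.373); p₂ = 0.067 (0.018, 0.213); d = 0.133. Lower = 0.133 − √(0.105² + 0.147²) = −0.047. Upper = 0.133 + √(0.173² + 0.048²) = 0.313. Fisher p = 0.25; interval −5 to +31 points.
- *5/30 v 0/30.* p₁ = 0.167 (0.073, 0.336); p₂ = 0 (0, 0.114); d = 0.167. Lower = 0.167 − √(0.093² + 0.114²) = 0.020. Upper = 0.167 + 0.169 = 0.336. Fisher p = 0.052; interval +2 to +34 points. The test just misses 0.05 while the interval lies wholly above zero.
- *3/30 v 3/30.* d = 0; interval −17 to +17 points. Identical observed rates still do not exclude a 17-point excess.
- *0/30 in one arm.* Exact two-sided 95% upper limit = 1 − 0.025^(1/30) = 11.6%.

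**3. Continuous measures.** For a standardized difference of 0.5 (an assumed value), two-group power is 48% with 30 per arm. If the 25% loss in section F.2 applied in full, 30 × 0.75 = 22.5 per arm would remain, and power with 22 per arm is 37%. That loss figure includes unusable MRS scans, and the ANOVAs may use the last available value, so the number analysed could be nearer 30.

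**4. Scale of a confirmatory safety claim.** With both rates at 10%, one-sided 0.025 and 80% power, excluding a margin δ needs n = (1.96 + 0.84)² × 2 × 0.1 × 0.9 / δ² per arm: 142 for 10 points, 63 for 15 and 36 for 20. A trial of this size can estimate safety differences but could confirm only a wide margin.

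**The case against.** A reader might infer that the plan will treat p>0.05 as proof of safety. The documents do not say so. Prediction 3 speaks only of examining group differences and gives no rule. Elsewhere in section E.b the plan does act on non-significance: Prediction 2 uses it to decide on T-scores for those aged 19 to 21, and Prediction 4 takes a non-significant direct effect as consistent with complete mediation. Neither passage concerns safety.

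A reader might also infer that the tests would miss nearly every real excess. That is too strong. It depends on the size of the excess and the placebo rate, and power passes one half for some large gaps.

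Three further points stand in the plan's favour:

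- Percentages for each AE are planned, so a reader who knows the arm sizes could derive a risk difference and interval for any single event.
- Aim 1 describes the data as pilot data, and low power for AE comparisons is normal in a pilot. No larger sample is called for here.
- Safety during the trial does not rest on these tests. There are weekly AE assessments with a structured questionnaire, independent causality assessment, and DSMB review of each serious event and, six-monthly, of all events.

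These points lower the stakes without closing the gap. Monitoring protects participants during the trial but does not settle how Prediction 3 is concluded. Pilot status favours estimation over testing. Percentages alone do not show what excess remains possible.

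**Conclusion.** The point holds in limited form. Prediction 3 is a claim of acceptable safety, its only comparative analyses are difference tests, and a non-significant result at 30 per arm could not support it. Under the assumed rates and two-sided 0.05, a 10-point excess over a 10% placebo rate would go undetected about 90% of the time with Fisher, and a 20-point excess over the same rate about 63% of the time. Non-significant results can leave excesses of some 30 points open. The illustrative rates and the significance level are assumptions, and other values would move these figures.

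The small sample is not itself the defect, and nothing here bears on the power calculations to which section F.2 refers. The defect is the absence of an estimate and interval on which to base the conclusion. This is a cheap improvement.

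**What to change.** In section E.b, Prediction 3:

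1. Make the primary safety comparison the risk difference with a 95% confidence interval (Newcombe, for example) for each AE, for serious AEs and for discontinuations.
2. For laboratory values and vital signs, report the between-group mean difference in change with a 95% interval.
3. Keep the Fisher, chi-square and ANOVA results as descriptive, and state that p>0.05 is not evidence of safety.
4. Word the Prediction 3 conclusion as pilot estimates, giving the range of excess risk that the data do not exclude. Telling readers to rely on upper limits without a margin would leave the same gap, and a margin tight enough to be useful is probably out of reach at this size, so a descriptive conclusion is the proportionate choice.

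The cost is a few lines of analysis-plan text. The data, sample and visits are unchanged. The downside is a more modest safety statement.
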